8.1.3 Response Criteria

Radiological response will be defined as per the RECIST criteria. Treatment outcomes will be defined as:

- Complete response (CR): complete resolution of all tumor lesions.
- Partial response (PR): at least a 30% decrease in the sum of the longest diameter of the target lesions (primary tumor and lymph nodes).
- Stable disease (SD): patients with changes that would not qualify as partial responses or progressive diseases.
- Progressive disease (PD): at least a 20% increase in the sum of the longest diameter of the target lesions.

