8.2 Time-to-Event Measures

The following definitions for time-to-event measures will apply:

- Duration of Tumor Response is measured from the date of the first objective assessment of PR or CR to the first date of disease relapse or death from any cause.
- Time to Progression is measured from the date of enrollment to the first date of radiographic progression of disease per RECIST 1.1 criteria.

9. Adverse Event Reporting

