10.2 Efficacy Analysis

The primary endpoint will be overall response rate. As noted above, 4 or more observed responses among 29 patients would be considered potentially efficacious and would justify further study. Responses include both complete and partial responses, as defined by RECIST 1.1 criteria. Duration of response and time to progression will be reported as median values. The disease control rate (DCR), defined as the stable disease + partial response rate will be calculated. Toxicity rates will be described as the overall percentage of patients experiencing Grade 3 or higher toxicity.

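### Followed literally, the Section 8.1.3 outcome list counts a patient with a new lesion and stable targets as disease control, and the event ending response duration is undefined (minor)

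*Combined protocol and SAP*

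**What the plan says.** Section 8.1.3 opens with "Radiological response will be defined as per the RECIST criteria. Treatment outcomes will be defined as" and then lists four outcomes. No RECIST version is given there. Three of the four bullets matter here:

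- Progression: "Progressive disease (PD): at least a 20% increase in the sum of the longest diameter of the target lesions".
- Partial response: "at least a 30% decrease in the sum of the longest diameter of the target lesions (primary tumor and lymph nodes").
- Stable disease: "patients with changes that would not qualify as partial responses or progressive diseases".

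Other sections name a version. Section 10.2 says of the primary endpoint: "Responses include both complete and partial responses, as defined by RECIST 1.1 criteria". Section 8.2 says: "Time to Progression is measured from the date of enrollment to the first date of radiographic progression of disease per RECIST 1.1 criteria". Section 7.5 uses RECIST 1.1 for removal from study on progression.

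Two endpoints name no standard in their own sentences. Section 10.2 says: "The disease control rate (DCR), defined as the stable disease + partial response rate will be calculated". In Section 8.2, duration of response runs "to the first date of disease relapse or death from any cause".

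Section 8.1.2 takes target lesions from all measurable disease and makes the baseline sum of longest diameters the reference for tumour response. It also requires non-target lesions to be followed for presence or absence.

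**The concern.** The protocol tells assessors to use a written list, and elsewhere to use a named standard, without saying which prevails where they differ. The list matters most where no standard is named alongside the endpoint, which is the case for stable disease (hence DCR) and the end of response duration.

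Taken at its word, the list lets a patient whose disease has spread to a new site count as controlled. It also leaves open how much regrowth ends a response. Because withdrawal follows RECIST 1.1, a patient could be taken off study for progression and still be tabulated as disease control. The stake is the meaning of two descriptive results in a single-arm, open-label trial, not the go/no-go decision.

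**Working it through.** **The plan's own figures first.** For the two-stage design in Section 10.1 (stop at 0 of 10; 4 or more of 29 is success):

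- Early stopping probability at 5%: 0.95^10 = 0.599 (stated 0.60).
- Expected size at 5%: 10 + 19 × (1 − 0.5987) = 17.62 (stated 17.6).
- Exact type I error is 0.0468 and exact power is 0.8011, within the stated limits.
- 3/29 = 10.3%, as stated.

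The design is correct, and nothing below alters it.

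**Literal classification.** Take a patient whose target sum is unchanged and who develops a new lesion.

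| Rule in 8.1.3 | Test | Met? |
|---|---|---|
| Complete response | all lesions gone | no |
| Partial response | target sum down 30% or more | no |
| Progression | target sum up 20% or more | no |
| Stable disease | neither partial response nor progression | yes |

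The patient enters DCR. The same happens if a non-target lesion clearly worsens, although Section 8.1.2 has those lesions followed. Section 5.1 accepts a new lesion as one form of evidence of progression at entry, so the protocol itself regards new lesions as informative.

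**Size for DCR.** This assumes all treated patients form the denominator.

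- Full enrolment: 1/29 = 3.4 points per misclassified patient.
- Stop after stage 1: 1/10 = 10 points per patient.

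The number of such patients is not given and cannot be derived.

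**Complete responders.** If the four categories are mutually exclusive, stable disease plus partial response leaves out complete responses. Each one lowers DCR by 1/29 = 3.4 points. This cannot arise in a trial stopped at 10, because stopping requires no responses.

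**Reference sum for progression.** Section 8.1.2 gives the baseline sum as the reference for response and no separate one for progression. Assume a baseline of 100 mm falling to 70 mm:

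- Against baseline, progression needs 1.2 × 100 = 120 mm, a regrowth of 120/70 − 1 = 71%.
- Against the smallest sum, it needs 1.2 × 70 = 84 mm, a regrowth of 20%.

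Both readings are open if relapse in Section 8.2 is taken to mean the 8.1.3 progression rule. The lesion sizes are assumed, to show the range.

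**Partial response wording.** The parenthetical restricts targets to the primary tumour and nodes. Section 8.1.2 draws them from all measurable lesions, and Section 5.1 admits metastatic disease. The two do not fit.

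**Nodes.** Sections 5.1 and 8.1.1 qualify a node by short axis; Sections 8.1.2 and 8.1.3 sum longest diameters. Both can be applied together, so this is a point to check against the named standard.

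**The case against.** The best defence is that RECIST 1.1 is already in force. It is the only version in the reference list, Section 5.1 uses it for measurability, and Sections 7.5, 8.2 and 10.2 name it for withdrawal, time to progression and response. Section 8.1.3 itself begins by deferring to RECIST. Since stable disease is defined by what is not partial response or progression, it can be read as inheriting the same standard, and relapse on study would ordinarily be the RECIST 1.1 progression that triggers withdrawal. DCR is not a listed objective and carries no threshold. The entry criterion is no template for on-study progression either, because it also accepts clinical deterioration.

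Much of this stands. The missing version number is not a real ambiguity, and the baseline sum does supply a reference for response. What remains is that Section 8.1.3 states in terms that outcomes are defined by its list, and nothing overrides that for stable disease or for the end of response duration.

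A reader might go further and infer that the primary result is at risk, since one changed call separates 3/29 from 4/29. The documents do not support that: the response endpoint names RECIST 1.1, and no rate of changed calls is given. Nor do they support calling the node rules a contradiction. The text of RECIST 1.1 is not reproduced, so no statement is made on how far the local list departs from it.

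**Conclusion.** The point holds at minor severity. The literal progression and stable-disease rules give a wrong classification for a patient with a new lesion and stable targets, and that classification feeds DCR. The event ending response duration is undefined, the partial response parenthetical does not fit the target-lesion rule, and DCR omits complete responders.

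The size is 3.4 DCR points per affected patient, or 10 points per new-lesion patient if the trial stops at 10. This assumes that assessors follow the 8.1.3 list and that the patient has no earlier assessment already counting as control; the protocol does not say whether DCR uses best response. For response duration, the two readings of the reference sum put progression at 84 or 120 mm in the assumed example; no effect on the median can be derived.

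Response rate, time to progression and withdrawal are affected only if the list is used in place of the standard they name.

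**What to change.** - **Section 8.1.3 and the primary objective (Section 3):** state that RECIST 1.1 governs complete response, partial response, stable disease and progression for every endpoint. Delete the four local bullets, including the parenthetical on primary tumour and nodes.
- **Sections 8.1.1 and 8.1.2:** make node measurement and the reference sum follow that standard.
- **Section 8.2:** end duration of response at progression by that standard or death.
- **Section 10.2:** define DCR as CR + PR + SD.
- **Sections 4, 6.2.2 and 7.5:** the treatment-continuation and withdrawal passages must be reconciled to the single definition. No stopping rule is proposed here.

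The cost is wording only; 29 patients and the 4-response cut-off stay. DCR and response duration may look slightly less favourable, though each complete responder now counted adds 3.4 points to DCR. One limit remains: Section 7.2 schedules CT of known disease sites, so new lesions elsewhere could still be missed.

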8.2 Time-to-Event Measures

The following definitions for time-to-event measures will apply:

- Duration of Tumor Response is measured from the date of the first objective assessment of PR or CR to the first date of disease relapse or death from any cause.
- Time to Progression is measured from the date of enrollment to the first date of radiographic progression of disease per RECIST 1.1 criteria.

9. Adverse Event Reporting

9.1 Adverse Events

Investigators are responsible for monitoring the safety of patients who have entered this study and for alerting the Cancer Consortium IRB to any event that seems unusual in accordance with IRB policy. The investigator is responsible for the appropriate medical care of patients during the study. The investigator remains responsible to follow, through an appropriate health care option, adverse events that are serious or that caused the patient to discontinue before completing the study. The patient should be followed until the event resolves or stabilizes. Frequency of follow-up is left to the discretion of the investigator.

Safety measurements that will be used in the study include physical examinations and clinical laboratory tests (hematology and blood chemistries). The adverse event will be graded for toxicity using the NCI CTC version 4.0. Toxicity assessment will occur at each monthly treatment visit, see Schedule of Events, Appendix 1. Any adverse events leading to a treatment interruption or dose reduction along with all adverse events that are grade 3 and higher will be recorded in the CRF.

9.2 Definition of an Adverse Event

The definitions of adverse events (AEs) and serious adverse events (SAEs) are given below.

An adverse event is the development of an undesirable medical condition or the deterioration of a pre-existing medical condition following or during exposure to a pharmaceutical product, whether or not considered causally related to the product. An undesirable medical condition can be symptoms (e.g., nausea, chest pain), or signs (e.g., tachycardia, enlarged liver).

9.3 Serious Adverse Events

An event that fulfills at least one of the following criteria will be designated a serious adverse event (SAE). SAEs will be reported to the Cancer Consortium IRB per Cancer Consortium policy/procedure.

- Results in death
- Requires initial inpatient hospitalization or prolongation of existing hospitalization
- Is immediately life-threatening
- Results in severe or permanent disability or incapacity
- Is a congenital abnormality or birth defect
- Any other important medical event that may jeopardize the subject or requires medical intervention to prevent one of the outcomes listed above.

Any events that are unequivocally due to progression of disease should not be reported as a serious adverse event.

9.4 Adverse Event Reporting Requirements

Adverse events will be collected after the patient has taken the first dose of study drug. After discontinuation from treatment, patients must be followed for all existing AEs for 30 calendar days after the last dose of study drug or until another anti-cancer therapy is initiated.

Prior to beginning study treatment, study site personnel will note the occurrence and nature of each patient's medical condition(s). During the study, site personnel will again note any change in the condition(s) and/or the occurrence and nature of any adverse events. Toxicities are to be graded according to the NCI CTC version 4.0.

A description of the event, including its date of onset and resolution, any action taken should be provided along with the investigator's assessment of causality. An event that is due to unequivocal progression of disease should not be reported as an AE. Any adverse events leading to a treatment interruption or dose reduction along with all grades 3 and higher adverse events must be recorded on a case report form (CRF).

To ensure patient safety, every SAE, regardless of suspected causality, occurring after the patient has initiated study therapy and until 30 days after the patient has stopped study treatment must be reported to Eisai within 24 hours of learning of its occurrence. Any SAEs experienced after this 30-day period should only be reported to Eisai if the investigator suspects a causal relationship to the study drug.

10. Data Analysis/Statistical Methods

10.1 Sample Size Determination

This is an open-label single-arm phase II study. We will utilize the optimal two-stage Simon design, which minimizes the expected number of patients enrolled under the null hypothesis and given various other assumptions [Simon]. The null hypothesis is that the true response rate is 5% and the alternative hypothesis is that the true response rate is 20%. If we additionally set the significance level to 0.05 (or less) and the power to be at least 80% ($p_0 = 0.05$, $p_1 = 0.20$, $a = 0.05$, $b = 0.20$), then Simon's design dictates that 10 subjects be treated in the first stage. If there are no responses among these 10, the study will be terminated due to lack of efficacy (i.e., this will be considered reasonably strong evidence against the alternative hypothesis that the response rate is 20% or more). If at least one response is observed among these 10, an additional 19 subjects will be recruited for a total of 29 subjects. If 3 or fewer responses are seen among the 29 (an observed response rate of 10.3% or less), the regimen will be deemed to be not sufficiently efficacious for further study. Four or more responses among the 29 will be viewed as sufficient evidence to deem the regimen as potentially efficacious (i.e., reasonably strong evidence that the true response rate is greater than 5%). The expected number of patients to be enrolled under the null hypothesis that the true response rate is 5% is 17.6, and the probability of terminating early in this scenario (after the first stage, i.e., if no responses are seen in the first 10 patients) is 0.60.

10.2 Efficacy Analysis

The primary endpoint will be overall response rate. As noted above, 4 or more observed responses among 29 patients would be considered potentially efficacious and would justify further study. Responses include both complete and partial responses, as defined by RECIST 1.1 criteria. Duration of response and time to progression will be reported as median values. The disease control rate (DCR), defined as the stable disease + partial response rate will be calculated. Toxicity rates will be described as the overall percentage of patients experiencing Grade 3 or higher toxicity.

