1.2 Systemic therapy for advanced refractory and metastatic SGC

There is no current standard of care for palliative chemotherapy in patients with advanced SGC. A recent review cited 12 small trials reporting the use of chemotherapy for salivary gland carcinomas [Laurie]. In general, objective responses to any cytotoxic agent or regimen are infrequent and stabilization of disease is more commonly observed. Agents with activity include cisplatin, mitoxantrone, vinorelbine, epirubicin, and paclitaxel. Combination chemotherapy also appears to be effective. The only randomized clinical trial done in this cancer demonstrated a higher response rate with cisplatin and vinorelbine compared to vinorelbine alone [Airoldi]. Data is insufficient to conclude that combination chemotherapy is superior to single agent therapy and combination therapy certainly has more toxicity. Despite scientific rationale for the use of molecular targeted agents such as imatinib (c-kit) [Hotte], gefitinib (EGFR), and trastuzumab (HER2) [Agulnik], the results of these agents in phase II clinical trials have been disappointing.

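### Section 10.2 defines the disease control rate as stable disease plus partial response and leaves out complete response

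*Combined protocol and SAP*

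**What the plan says.** Section 10.2 (Efficacy Analysis) gives the only definition of DCR: "The disease control rate (DCR), defined as the stable disease + partial response rate will be calculated". Two sentences earlier, the same section describes the primary endpoint: "Responses include both complete and partial responses, as defined by RECIST 1.1 criteria".

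Section 8.1.3 (Response Criteria) sets out four outcomes: CR, PR, SD and PD. The three that matter here are:

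- The first outcome listed is worded as follows: "Complete response (CR): complete resolution of all tumor lesions"
- The second has its own entry and sets no upper limit on shrinkage: "Partial response (PR): at least a 30% decrease in the sum of the longest diameter of the target lesions"
- The third is a remainder category: "Stable disease (SD): patients with changes that would not qualify as partial responses or progressive diseases"

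Section 8.2 names both kinds of response when it defines duration: "Duration of Tumor Response is measured from the date of the first objective assessment of PR or CR".

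DCR does not appear among the primary, secondary or exploratory objectives in Section 3. No hypothesis or threshold is attached to it.

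**The concern.** Where the protocol means to include complete responders, it says so: in the primary endpoint (10.2), in duration of response (8.2) and in the list of outcomes (8.1.3). The DCR sentence names PR and SD only. If the four outcomes are separate categories, the best possible result is left out of a rate meant to capture patients whose disease is controlled. A patient whose best response improved from PR to CR would lower the DCR. If every response were complete, DCR would reduce to the SD rate.

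At stake is one reported descriptive figure. It is nevertheless one that readers may well look at, because Section 1.2 says of this disease: "In general, objective responses to any cytotoxic agent or regimen are infrequent and stabilization of disease is more commonly observed".

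**Working it through.** **1. The plan's own figures.** Section 10.1 gives stage 1 n = 10, total n = 29, stop on 0 responses, four or more of 29 as promising, and response rates of 5% (null) and 20% (alternative).

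- Probability of early termination at 5%: 0.95^10 = 0.5987 (plan: 0.60).
- Expected enrolment at 5%: 10 + 19 × (1 − 0.5987) = 17.62 (plan: 17.6).
- Exact type I error is 0.0468 and power is 0.8011, within the stated limits of 0.05 and 80%.

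The design reproduces. It uses CR + PR, so nothing below changes it. The plan states no numerical DCR.

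**2. Difference between the two definitions.**

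- As written: (PR + SD)/n.
- With CR named: (CR + PR + SD)/n.
- Difference: CR/n.

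At n = 29 this is 1/29 = 3.4 percentage points per CR.

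An example with assumed counts, 1 CR + 3 PR + 10 SD among 29, gives (3 + 10)/29 = 13/29 = 44.8% as written and (1 + 3 + 10)/29 = 14/29 = 48.3% with CR named.

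**3. Stop at stage 1.** Section 10.1 states: "If there are no responses among these 10, the study will be terminated due to lack of efficacy". No responses means no CRs, so the two definitions then agree.

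**4. How often it would matter.** The documents give no CR share of responses. The range of 5% to 25% used here is an assumption. Let p be the true response rate, f the CR share, c = p × f, and PET = (1 − p)^10, which is 0.599 at p = 0.05 and 0.107 at p = 0.20.

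The chance that the trial passes stage 1 and has at least one CR among 29 is

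(1 − PET) − [(1 − c)^10 − PET] × (1 − c)^19.

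The average understatement over all trials, counting stage 1 stops as zero, is

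f × p × (29 − 19 × PET)/29.

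| p | f | Chance DCR changes | Average understatement (points) |
|---|---|---|---|
| 0.05 | 0.05 | 0.042 | 0.15 |
| 0.05 | 0.25 | 0.178 | 0.76 |
| 0.20 | 0.05 | 0.234 | 0.93 |
| 0.20 | 0.25 | 0.707 | 4.65 |

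The last row in full:

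- c = 0.20 × 0.25 = 0.05.
- Chance: 0.893 − (0.599 − 0.107) × 0.95^19 = 0.707, using unrounded values.
- Average: 0.25 × 0.20 × (29 − 19 × 0.107)/29 = 4.65 points.

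A simulation of 1,000,000 trials per setting agreed with all four rows to within 0.001 on the chance and to the figures shown on the average.

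**The case against.** The strongest reply is that, taken literally, the definition already covers CR. Section 8.1.3 puts no upper limit on the shrinkage that makes a PR, so a CR could satisfy it. SD is the remainder after PR and PD, so a CR that was somehow not a PR would fall there. Together the two routes take in every complete responder, and Section 8.1.3 never says that its outcomes are mutually exclusive. On this view the sentence is ambiguous rather than wrong.

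It is true that mutual exclusivity is inferred and not stated. But the literal route makes the four listed outcomes overlap, classes a complete responder as partial or stable, and makes the separate mention of complete responses in Section 10.2 redundant. It also leaves two analysts free to report different DCRs from the same data.

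A second objection is that the ranges in step 4 rest on a CR share with no support in the documents. That stands. At an assumed share of 1%, the chance falls to 0.9% (true rate 5%) or 5.2% (true rate 20%), and the average differences fall to 0.03 and 0.19 points. At a share of 0% both are nil. Section 1.2 calls objective responses infrequent, so CRs may be few.

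A third is that the consequence is small. That also stands. If best response is tabulated by category under the general rule for categorical data in Section 10.3, a reader could rebuild the DCR, although Section 10.3 does not specifically call for that table.

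**Conclusion.** The point holds, as a minor correction. On the natural reading that the outcomes in Section 8.1.3 are separate categories, the stated rule gives a DCR that is too low whenever a CR occurs. The firm size is 3.4 percentage points per CR at n = 29, and zero without a CR. The chances and averages in step 4 are conditional on the assumed CR share and only show the possible scale. The effect grows with the response rate, so it is largest in the scenario the trial is designed to detect. The trial's conclusion on efficacy does not depend on it.

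**What to change.** In Section 10.2, define the disease control rate as the sum of the complete response, partial response and stable disease rates. This adds one term to one sentence. Sample size, analysis set, data collection and decision rule stay as they are. Making the change before the analysis avoids settling the definition after the responses are known.
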